In subjects who experience recurring bleeding episodes, the Investigator and Medical Monitor will discuss whether to resume prior FVIII prophylaxis. Subjects who do not respond to BMN 270 treatment (ie, treatment failure manifesting as failure to achieve FVIII activity \geq 5 IU/dL by Week 52 and inability to maintain independence from prophylactic FVIII replacement therapy due to joint bleeding episodes, in the judgment of the Investigator) may, at the Investigator's discretion and after discussion with the Medical Monitor or Sponsor-designated Data Monitor, follow an abbreviated visit schedule after Week 52 of the study by attending only the Q12W and End of Year visits during Years 2-5. Subjects who are not attending the Q4W/Q6W visits during Years 2-5 may receive a scheduled monthly follow-up telephone call from the site to ask about adverse events, concomitant medications, and bleeding events/FVIII replacement usage.

There will be an ongoing review of individual subject safety by the Medical Monitor, and both safety and efficacy data by the DMC. Patients will receive prophylactic corticosteroids with tapering of the dosage based upon consideration of ALT values, FVIII activity levels, and as indicated, consultation with the Investigator and the Medical Monitor. Reactive oral corticosteroids may be initiated if a subject's ALT values increase from baseline levels, after consultation between the Investigator and the Medical Monitor (refer to Section 9.4.8.2).

In case of a safety concern, additional unscheduled laboratory tests may be performed locally (at the Investigator's discretion) in order to facilitate timely and appropriate clinical management decisions; where possible, a matched sample for testing at the central laboratory should be collected (using the Unscheduled Visit lab kit) at the same time as the local unscheduled sample.

Any safety signal may trigger a review of the data and possible additional immunogenicity studies or other diagnostics deemed necessary that include an assessment of cellular immune responses using collected peripheral blood mononuclear cells (PBMCs).

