9.3.1 Inclusion Criteria

Individuals eligible to participate in this study must meet all of the following inclusion criteria:

1. Males \geq 18 years of age with hemophilia A and residual FVIII levels \leq 1 IU/dL as evidenced by medical history, at the time of signing the informed consent.
2. Must have been on prophylactic hemophilia therapy for at least 12 months prior to study entry. High-quality, well-documented historical data concerning bleeding episodes and hemophilia therapy usage over the previous 12 months must be available.
3. Treated/exposed to FVIII concentrates or cryoprecipitate for a minimum of 150 exposure days (EDs).

4. Willing and able to provide written, signed informed consent after the nature of the study has been explained and prior to any study-related procedures.
5. No previous documented history of a detectable FVIII inhibitor, and results from a Bethesda assay or Bethesda assay with Nijmegen modification of less than 0.6 Bethesda Units (BU) (or less than 1.0 BU for laboratories with a historical lower sensitivity cutoff for inhibitor detection of 1.0 BU) on 2 consecutive occasions at least one week apart within the past 12 months (at least one of which should be tested at the central laboratory).
6. Sexually active participants must agree to use an acceptable method of effective contraception, either double-barrier contraception (ie, condom + diaphragm; or condom or diaphragm + spermicidal gel or foam) or their female partner either using hormonal contraceptives or having an intrauterine device. Participants must agree to contraception use for at least 12 weeks post-infusion; after 12 weeks, subjects may stop contraception use only if they have had 3 consecutive semen samples with viral vector DNA below the limit of detection.
7. Willing to abstain from alcohol consumption for at least the first 52 weeks following BMN 270 infusion.

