9.4.8.1 Concomitant Hemophilia Treatments

To avoid breakthrough bleeding, subjects will only discontinue exogenous prophylactic FVIII replacement therapy 4 weeks following infusion of BMN 270 or if FVIII activity has consistently increased above 5 IU/dL, whichever is earlier. Subjects previously receiving emicizumab, given its approximate 1-month half-life, will remain on emicizumab prophylaxis until BMN 270 infusion, with their final dose administered prior to Day 1.

FVIII replacement therapy can always be taken as needed by the subject for treatment of an acute bleeding episode; the subject must carefully record his treatment and bleeding episodes in his diary. Prophylactic FVIII use can be used on a case-by-case basis and in consultation with the Medical Monitor to prevent bleeding in extenuating circumstances (eg peri-operative).

In addition, information on FVIII usage and bleeding episodes by medical history must be well-documented and available and will be collected from subjects for the 12-month period immediately preceding study enrollment. Further information on the details that should be provided as part of the subject's well-documented medical and FVIII usage history are provided in the Investigator Site File Binder.

In order to enable rigorous comparisons of pre-study versus on-study FVIII usage and bleeding episodes, the Medical Monitor will review each screened patient's prior bleed and hemophilia medication logs to determine if they are of "high-quality". Elements that will be assessed to judge the quality of such historical data may include, but are not limited to, the following:

- Date, type (eg, joint, muscle, other), location of bleeds
- Date, name, dose (calculated in IU/kg), and reason for use (eg, usual prophylaxis, one-time prophylaxis, treatment for bleed, surgery) of hemophilia medications.

9.4.8.2 Corticosteroid Treatment and/or Alternative Immunosuppressive Agent Treatment of Elevated Hepatic Transaminases

Prior to dosing, all subjects must be screened per steroid prescription guidelines to ensure the subject is eligible to receive corticosteroid treatment as outlined in the protocol. Refer to corticosteroid prescription guidelines for recommended monitoring for, and management of, potential side effects of corticosteroids, including guidance on medications that should be avoided during corticosteroid treatment.

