9.7.3 Secondary Efficacy Variables

9.7.3.1 Factor VIII Replacement Therapy/Bleeding Episodes

Secondary efficacy variables include:

- Change in the annualized utilization (IU/kg/year) and infusion (number/year) rates of exogenous FVIII replacement therapy from Week 5 post-BMN 270 infusion to last visit by data cutoff (for Week 52 analysis) from the baseline number and utilization of exogenous FVIII replacement therapy for subjects receiving FVIII prophylaxis during the 12 months prior to study entry, or change in administration of exogenous FVIII replacement therapy from Week 27 post-BMN 270 infusion to last visit by data cutoff (for Week 52 analysis) for subjects receiving prior emicizumab prophylaxis.
- Change in the annualized number of bleeding episodes requiring exogenous FVIII replacement treatment (annualized bleeding rate, ABR) from Week 5 post-BMN 270 infusion to last visit by data cutoff (for Week 52 analysis) for subjects receiving prior FVIII prophylaxis, or from Week 27 post-BMN 270 infusion to last visit by data cutoff (for Week 52 analysis) for subjects receiving prior emicizumab prophylaxis, compared to the baseline ABR during the 12 months prior to study entry.

Subjects must have high quality documented historical data available concerning previous bleeding episodes and hemophilia treatment over the previous 12 months in order to be eligible to enroll in the study. During the study, subjects will be asked at each study visit to report the use of factor replacement therapy and the number of bleeding episodes since the previous visit. This information will be captured on the subject's diary or other subject records. Subjects will be encouraged to discuss any bleeding episodes with the Investigator and attempt to objectively assess any reported bleeds through use of ultrasound or non-invasive imaging.

Subjects are strongly encouraged to immediately consult Investigator for guidance regarding exogenous FVIII administration for suspected bleeds or bleeding episodes within the first 30 days post-BMN 270 infusion.

In subjects who experience recurrent bleeding episodes, the Investigator and Medical Monitor will discuss whether to resume prior FVIII prophylaxis or use of emicizumab.

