14.3 Secondary Efficacy Endpoints

The analyses of the secondary efficacy endpoints will be descriptive. Mean and associated 95% confidence interval will be provided for the following secondary endpoints, where the baseline value will be derived from the data in the approximately 12-month period prior to BMN 270 infusion:

- For subjects receiving FVIII prophylaxis prior to study entry, change from baseline in the annualized utilization (IU/kg/year) of exogenous FVIII replacement therapy from Week 5 post BMN 270 infusion to last visit by data cutoff (for Week 52 analysis); and separately, for subjects receiving prior emicizumab prophylaxis, change from baseline in the annualized utilization (mg/kg/year) of emicizumab from Week 27 post BMN 270 infusion to last visit by data cutoff (for Week 52 analysis)
- For subjects receiving FVIII prophylaxis prior to study entry, change from baseline in the annualized infusion rate (number/year) of exogenous FVIII replacement therapy from Week 5 post BMN 270 infusion to last visit by data cutoff (for Week 52 analysis); and separately for subjects receiving prior emicizumab prophylaxis, change from baseline in the annualized utilization (mg/kg/year) of emicizumab from Week 27 post BMN 270 to last visit by data cutoff (for Week 52 analysis) infusion
- Change from baseline in the annualized number of bleeding episodes (number/year) requiring exogenous FVIII replacement treatment from Week 5 post-BMN 270 infusion to last visit by data cutoff (for Week 52 analysis) for subjects receiving prior FVIII prophylaxis, or from Week 27 post-BMN 270 infusion to last visit by data cutoff (for Week 52 analysis) for subjects receiving prior emicizumab prophylaxis from baseline

Mean change from baseline and associated 95% confidence interval will be calculated for the total score of Haemo-QoL-A at Week 52 post-BMN 270 infusion as well.

The missing value of the change for annualized utilization and annualized infusion rate will be imputed as 0. The missing value of the change for annualized number of bleeding episodes will be imputed using the median value of the changes of all observed cases.

A sensitivity analysis is planned to analyze ABR using a generalized linear mixed model assuming negative binomial as the underlying distribution. The model will include period (pre- to post-BMN 270 infusion) as the only factor, repeated within subject. The actual

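### Prophylaxis is stopped by rule before the therapy-use windows open, so a fall in use cannot by itself be read as a BMN 270 effect; for prior-emicizumab subjects Section 14.3 scores some failures as full success

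*Protocol*

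**What the plan says.** Inclusion criterion 2 (Protocol 9.3.1) requires that each subject "Must have been on prophylactic hemophilia therapy for at least 12 months prior to study entry". Under Section 9.4.8.1, "subjects will only discontinue exogenous prophylactic FVIII replacement therapy 4 weeks following infusion of BMN 270", or earlier if FVIII activity is consistently above 5 IU/dL. Response can bring the stop forward, but lack of response does not postpone it. Subjects on emicizumab "will remain on emicizumab prophylaxis until BMN 270 infusion, with their final dose administered prior to Day 1".

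Section 14.3 (Amendment 2 text) makes change in use a secondary efficacy endpoint. For prior-FVIII subjects it is IU/kg/year and infusions/year of exogenous FVIII from Week 5 to the last visit by data cutoff. For prior-emicizumab subjects it is "change from baseline in the annualized utilization (mg/kg/year) of emicizumab from Week 27 post BMN 270 infusion to last visit by data cutoff". The infusion-rate bullet repeats that same mg/kg/year quantity for them, so 14.3 contains no FVIII-use measure for this group. For all of these endpoints, "the baseline value will be derived from the data in the approximately 12-month period prior to BMN 270 infusion".

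Section 9.7.3.1, which defines the secondary variables, instead gives prior-emicizumab subjects a change in exogenous FVIII administration from Week 27. The two places that deal with recurrent bleeding also differ. In 9.1, "the Investigator and Medical Monitor will discuss whether to resume prior FVIII prophylaxis"; in 9.7.3.1, the same parties "will discuss whether to resume prior FVIII prophylaxis or use of emicizumab".

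The objectives in Section 8 describe the use results as the impact of BMN 270. Section 9.2 says there is no control group.

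**The concern.** A before-and-after comparison of therapy use is informative about the product only if use afterwards reflects need. Here the prophylactic part of use, which makes up most of the baseline, is removed by instruction before counting begins. What remains in the FVIII measure is bleed treatment, one-off prophylaxis and any prophylaxis resumed after a discretionary discussion. These do respond to failure, but they are measured against a baseline of routine prophylaxis.

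The emicizumab measure is weaker still. It registers failure only if emicizumab is the product that is restarted. A subject whose treatment fails and who goes onto FVIII prophylaxis, the only resumption that 9.1 mentions, contributes the best possible score.

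At stake is how a mean reduction and its 95% confidence interval, reported under an efficacy heading, would be understood.

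**Working it through.** **Plan's own figure.** The protocol gives no power or expected size for the use endpoints. Its only power figure, 85% for the primary endpoint, reproduces: one-sample t-test, n = 16, effect size 0.8, 1-sided 0.025, df = 15, noncentrality 0.8 × √16 = 3.2, power 84.8%. This point does not affect it.

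**FVIII infusion rate with no drug effect, prophylaxis never resumed.** Inputs:

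- Prophylaxis 2-3 times per week (Section 7.3), so B = 2 × 52 = 104 to 3 × 52 = 156 infusions/year.
- On-demand median ABR 4.5-18 (retrospective study) or 20-60 (prospective studies), both from Section 7.3.
- Infusions per treated bleed, k: not given in the protocol; assumed 1, 2 or 3.

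Change = ABR × k / B − 1. In each cell the first value is for B = 104 and the second for B = 156.

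| ABR | k = 1 | k = 2 | k = 3 |
|---|---|---|---|
| 4.5 | −95.7% / −97.1% | −91.3% / −94.2% | −87.0% / −91.3% |
| 18 | −82.7% / −88.5% | −65.4% / −76.9% | −48.1% / −65.4% |
| 20 | −80.8% / −87.2% | −61.5% / −74.4% | −42.3% / −61.5% |
| 60 | −42.3% / −61.5% | +15.4% / −23.1% | +73.1% / +15.4% |

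Ten of the 12 combinations lie between −42% and −97%. The two exceptions are ABR 60 with 2 or 3 infusions per bleed, where the change runs from −23% to +73%.

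**The same with prophylaxis resumed.** Weeks 5-52 are 48 weeks. If a subject is off prophylaxis for the first w of these weeks and then returns to the earlier rate, change = (w/48) × (ABR × k / B − 1). This ignores bleed treatment after resumption. For k = 1-2 the most favourable bracket is −97.1% and the least favourable +15.4%:

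- w = 4: −8.1% to +1.3%
- w = 12: −24.3% to +3.8%
- w = 24: −48.6% to +7.7%

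Utilization in IU/kg/year was not calculated, because the protocol gives no dose per infusion.

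**Emicizumab mg/kg/year with no drug effect.** Weeks 27-52 are 26 weeks. With v of those weeks free of emicizumab, change = −v/26:

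- never restarted (v = 26): −100%
- restarted 13 weeks into the window (v = 13): −50%
- back at the prior rate by Week 27 (v = 0): 0%
- moved to FVIII prophylaxis instead (v = 26): −100%, with the FVIII not counted anywhere in the 14.3 use endpoints

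**Passages side by side.** For the last subject, 9.7.3.1 would record the FVIII prophylaxis as use, while 14.3 would record complete cessation. Both cannot define the same secondary endpoint.

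**The case against.** A reader might infer that the use endpoints must show a large reduction even if BMN 270 does nothing, or that the fall comes wholly from the instruction. The documents do not support that. FVIII use counts every infusion for a bleed and any resumed prophylaxis, and both would be expected to rise if the product failed. The treatment-failure definition in 9.1 itself includes inability to stay off prophylactic FVIII. Depending on bleed rate, infusions per bleed and time to resumption, the no-effect change may be large, small or even positive, and the protocol does not fix the last two. Nor is −100% inevitable for emicizumab, because 9.7.3.1 allows it to be resumed, and it would then count.

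There are real mitigations. The secondary analyses are descriptive, with no hypothesis test. The only test is on FVIII activity. A missing change in use is imputed as 0, which works against the product. The late windows keep instructed prophylaxis and residual emicizumab out of the count. ABR is reported over the same windows and should rise without an effect: Section 7.3 puts the median at 1-4 on prophylaxis, against 4.5-18 or 20-60 on demand.

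These points limit the consequence but do not remove it. Imputing 0 affects missing values only, nothing in 14.3 ties the reading of use to ABR, and the emicizumab measure still cannot see a switch to FVIII prophylaxis.

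**Conclusion.** The point holds in a conditional form. Both use windows open after a stop that does not depend on response, so a fall from the prophylaxis baseline cannot by itself be read as an effect of BMN 270.

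For FVIII infusions, the fall with no effect is about 42-97% if prophylaxis is never resumed, over most of the protocol's on-demand bleed rates. It is at most about 8-24% if prophylaxis resumes after 4-12 weeks, and can vanish or reverse at an ABR near 60 with two or more infusions per bleed. These figures rest on an assumed 1-3 infusions per bleed (1-2 for the resumption cases).

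For prior-emicizumab subjects no such assumption is needed: under 14.3 the change is −100% unless emicizumab itself is restarted, so one kind of treatment failure is scored as full success. The conflict between 14.3 and 9.7.3.1 on which product is counted is a defect in the text whatever the size of the bias. The primary analysis is untouched.

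**What to change.** In Section 14.3:

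- Reconcile with 9.7.3.1 so that prior-emicizumab subjects have both exogenous FVIII use (IU/kg/year and infusions/year) and any emicizumab use reported from Week 27. The FVIII infusion rate replaces the repeated emicizumab mg/kg/year in the infusion-rate bullet.
- Report post-infusion use split by recorded reason: routine prophylaxis, one-time prophylaxis, bleed treatment, surgery or procedure.
- Add the proportion of subjects staying off routine prophylaxis of any kind to Week 52, with an exact 95% CI.
- State that the change in use is read together with ABR. Keep total use as a descriptive secondary measure.

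Sections 9.1 and 9.7.3.1 must also be reconciled on which prophylaxis may be resumed. No view is taken on which clinical rule is right, and no change to when prophylaxis stops or resumes is proposed.

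The cost is wording and a few extra tables. Reason for use is already an element of the historical medication logs (9.4.8.1), and the FVIII infusion eCRF pages already carry a use category (9.7.7.1). The downside for the sponsor is a less favourable reading of the headline reduction in use.

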The half-life for FVIII (12 to 18 hours for most approved products) necessitates frequent infusions, and although a major advance in the treatment of HA, it remains common for severe HA patients to continue to have multiple bleeding events on prophylactic therapy (median ABR of 1-4 with prophylaxis treatment in a recently published retrospective observational study ([Berntorp 2017](#)) and between 1-2 in 6 prospective FVIII interventional studies) and on-demand-only therapy (median ABR of 4.5-18 in a recently published retrospective study (Berntorp, 2017) and between 20-60 in 6 prospective FVIII interventional studies). The consequence of multiple bleeding events is the development of debilitating multiple-joint arthropathy and substantially increased risk of death. Chemical modification (eg, direct conjugation of polyethylene glycol (PEG) polymers) and bioengineering of FVIII (eg, FVIII-Fc fusion proteins) improve half-life by approximately 50%, and thus, show promise in reduced dosing and maintaining activity levels above a 1% trough for a greater proportion of the dosing interval. However, patients with severe HA who are treated with extended half-life FVIII remain dependent on multiple infusions to maintain critical levels of FVIII activity. There is therefore a strong unmet need for a fully preventive treatment of HA to give patients a FVIII level compatible with a normal and hemorrhage-free life.

[figure not shown]
Gene therapy offers the potential of disease-modifying therapy by continuous endogenous production of active FVIII following a single intravenous infusion of a vector encoding the appropriate gene sequence for long-term episomal expression. Hemophilia A is well-suited for a gene replacement approach because clinical manifestations are attributable to the lack of a single gene product (FVIII) that circulates in minute amounts (200 ng/ml) in the plasma. Tightly regulated control of gene expression is not essential, and even modest increases in the level of FVIII (any increase of the plasma level by 2 ng/ml induces an increase in activity of 1%) can ameliorate the severe form of hemophilia A. Thus, relatively small changes in endogenous FVIII activity can result in clinically relevant improvements in disease phenotype. Finally, the circulating FVIII response to gene transduction can be assessed using validated quantitative rather than qualitative endpoints that are easily assayed using established laboratory techniques.

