number of bleeding episodes will be used as the dependent variable with the time period adjustment (annualization) being implemented as the offset.

To assess the impact of missing data, analyses using observed case are planned as sensitivity analyses for the secondary endpoints. Multiple imputation methods may also be performed.

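### Filling a missing change in annualized bleeding rate with the observed median makes the reported 95% CI too narrow and ignores the subject's own baseline

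*Protocol*

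**What the plan says.** Protocol section 14.3 sets out the secondary endpoints, ABR among them, and states: "Mean and associated 95% confidence interval will be provided for the following secondary endpoints". It gives two rules for missing values. For the factor-use endpoints: "The missing value of the change for annualized utilization and annualized infusion rate will be imputed as 0". A missing change in ABR is instead to be "imputed using the median value of the changes of all observed cases". No reason is given for the difference.

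The post-infusion ABR window starts at Week 5 for subjects with prior FVIII prophylaxis and at Week 27 for those with prior emicizumab. It ends at the last visit by the data cutoff. The utilization and infusion-rate items treat the two groups separately; the ABR item and its imputation rule do not.

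The same section adds a negative binomial mixed model on actual bleed counts as a sensitivity analysis. On missing data it says that "analyses using observed case are planned as sensitivity analyses for the secondary endpoints", and then: "Multiple imputation methods may also be performed".

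**The concern.** Three properties follow from the rule as written.

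- **Precision.** Every missing subject receives the same value, close to the centre of the data. The sample SD shrinks while the divisor is the full n, so the interval overstates what is known.
- **Own baseline ignored.** The value is put on the change scale with no floor at minus the subject's baseline. Section 7.3 cites a "median ABR of 1-4 with prophylaxis treatment in a recently published retrospective observational study", and section 9.3.1 requires prophylaxis for the 12 months before entry. Low baselines are therefore to be expected, and an imputed reduction can exceed the number of bleeds the subject had to lose.
- **Pooling.** The median is taken over all observed cases, although the two prior-therapy groups have different windows and different baseline treatment.

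The mean and its interval are the main summary of bleeding in a study of about 20 subjects. The interval is the only statement of uncertainty attached to that mean.

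**Working it through.** **Inputs.** n = 16 is the minimum number of AAV5 antibody-negative subjects (section 14.8), who form the primary efficacy population (section 14.9). The protocol gives no precision figure for ABR. Its only related figure, 85% power for the primary endpoint, reproduces at 84.8% (noncentral t, 15 df, noncentrality 0.8 × √16 = 3.2) and is not in question. The number of missing ABR values is not stated, so 1, 2 and 3 are shown. ABR means and dispersion are assumptions.

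**Width of the interval.** Let k of n values be missing and let the imputed median equal the observed mean. The sum of squares is unchanged, so

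ratio of widths (imputed / observed-case) = √[(n−k−1)/(n−1)] × √[(n−k)/n] × t(n−1)/t(n−k−1), with t the 97.5% quantile.

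For n = 16, k = 2: √(13/15) × √(14/16) × 2.131/2.160 = 0.931 × 0.935 × 0.987 = 0.859.

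| Missing | n = 16 | n = 20 |
|---|---|---|
| 1 | 0.930 | 0.945 |
| 2 | 0.859 | 0.890 |
| 3 | 0.789 | 0.835 |

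**Illustrative data.** Take 14 observed changes: 0, 0, −1, −1, −2, −2, −3, −3, −3, −3, −5, −5, −7, −8 (sum −43, median −3), and 2 missing.

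| Rule | Mean | 95% CI | Width |
|---|---|---|---|
| Observed cases | −3.07 | −4.48 to −1.67 | 2.81 |
| Median | −3.06 | −4.27 to −1.86 | 2.41 |
| Zero | −2.69 | −4.02 to −1.36 | 2.66 |

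The median rule leaves the mean almost unchanged and removes 14% of the width (2.41/2.81 = 0.86).

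**Coverage.** Simulation with 40,000 replicates, n = 16, values missing at random. Counts are independent negative binomial with variance μ + 1.5μ², baseline mean 4, post-infusion mean 0.8.

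| Missing | Observed cases | Median rule | Loss (points) |
|---|---|---|---|
| 1 | 90.7% | 88.9% | 1.8 |
| 2 | 90.7% | 86.4% | 4.3 |
| 3 | 90.4% | 83.0% | 7.4 |

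Complete data already give only about 91%, because a t-interval is applied to skewed counts. Only the last column belongs to the imputation rule. With baseline mean 1.5, observed-case coverage is 94.0% and the losses are smaller: 1.4, 2.8 and 4.9 points.

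**Negative implied rates.** Implied post-infusion ABR = own baseline + median change. With a median change of −3, a subject with baseline 1 is assigned 1 − 3 = −2 bleeds per year. Across assumed baseline means of 1.5 to 5, 13% to 40% of imputed subjects received a negative rate.

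**Direction of the mean.** Gamma-Poisson counts with shape 0.8, baseline mean 3 and a 75% reduction give a true mean change of −2.25. With values missing at random, the median rule gives −2.19, −2.13 and −2.08 for 1, 2 and 3 missing, against −2.25 for observed cases. The distribution of changes is skewed, the median reduction is smaller than the mean reduction, and the estimate moves slightly towards zero. If instead the missing subjects had no benefit (first set of assumptions, baseline mean 4), the true mean is −2.80 with 2 missing and −2.60 with 3. The rule gives −3.01 and −2.93; observed cases give −3.20 and −3.21.

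**The case against.** The strongest reply is that little turns on this. "The analyses of the secondary efficacy endpoints will be descriptive", so there is no test and no type I error. The window runs to the last visit, so anyone followed past Week 5 (or Week 27) has an observed ABR. Section 9.3.1 requires a documented 12-month history, so baselines should be complete. Section 7.4 reports that none of 151 treated subjects left a study because of an adverse event, though it does not give other reasons for leaving. Two or three missing of 16 is a stress case, and with none missing the rule does nothing. All of this stands and limits the weight of the point.

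It can also be said that the observed-case analysis and the negative binomial model do not use the imputed value and so escape both the narrowing and the negative rates. That is true, but they are sensitivity analyses, and the main mean and interval keep the defect. Multiple imputation is only optional. Nor is the rule simply left to the SAP: section 14.3 already fixes it.

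A reader might infer that the rule biases ABR towards benefit, since early leavers receive a typical reduction while the factor-use endpoints receive zero. The documents do not support that as a general statement. It needs the added assumption that leavers did not benefit; with skewed counts missing at random the shift is the other way.

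A reader might also infer that copying the zero rule would cure the problem. Zero is equally a constant treated as data. In the 75%-reduction scenario its coverage was 85.1% and 80.9% with 2 and 3 missing, against 86.1% and 82.9% for the median rule.

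**Conclusion.** The point holds as a defect of precision and of form. If any ABR change is missing, the stated interval is too short: by about 7%, 14% and 21% relative to observed cases for 1, 2 and 3 missing of 16. That result is algebraic and assumes only that the median lies near the mean. The coverage losses of about 2, 4 and 7 points, and the share of negative implied rates, rest on assumed bleeding distributions; both are smaller when baseline bleeding is low. Negative rates would not be printed, because the change is what is analysed, but they show that the imputed value can be impossible for that subject.

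The credit given to early leavers is favourable only if they did not benefit. The unexplained contrast with the zero rule in the preceding sentence is real, but it is not evidence of bias in either direction. The effect is confined to subjects with no evaluable window, who are probably few, and to a descriptive endpoint. It is worth correcting because the correction is small.

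**What to change.** In section 14.3, and in the SAP, replace median imputation for the main ABR mean and interval with one of the following:

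- **Preferred:** multiple imputation of the post-infusion bleed count, from a negative binomial model with the subject's own baseline count, prior-therapy stratum and a log-time offset, combined by Rubin's rules. Imputing a count rules out negative rates, and including the stratum respects the two windows.
- **Simpler:** make the already planned observed-case analysis the main one.

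Both assume that leavers resemble similar subjects who stayed, so neither tests the no-benefit case. Add change = 0 as a sensitivity analysis for that purpose, and state that, as a single constant, it does not repair the interval.

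The cost is a few sentences and a wider interval when data are missing. For the observed-case option with n = 16, it is about 8%, 16% and 27% wider than under the median rule for 1, 2 and 3 missing (1/0.930, 1/0.859, 1/0.789). With nothing missing, the observed-case result is identical to the current one.
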